### 11.3.2. Dose number

- The study dose number is defined in reference to the number of study visits at which vaccination occurred. More specifically dose 1 refers to all vaccines administered at the first vaccination visit while dose 2 corresponds to all vaccinations administered at the second vaccination visit even if this is the first time a product is administered to the subject.
- Relative dose: the relative dose for an event (AE, medication, vaccination) is the most recent study dose given before an event. In case the event takes place on the day a study dose is given, the related dose will be that of the study dose, even if the event actually took place before vaccination. For instance, if an adverse event begins on the day of the study vaccination but prior to administration of the vaccine, it will be assigned to this dose. In case a study dose is not administered and an event occurs after the subsequent study dose (eg 2nd study dose), the relative dose of the event will be study dose associated to the subsequent study dose (eg dose 2).
- The number of doses for a product is the number of times the product was administered to a subject.
- The incidence per dose is the number of vaccination visits at which an event was reported among all vaccination visits.

### 11.3.3. Demography

- Age: Age at the reference activity, computed as the number of units between the date of birth and the reference activity. Note that due to incomplete date, the derived age may be incorrect by 1 month when month is missing from the birthdate. This may lead to apparent inconsistency between the derived age and the eligibility criteria/the age category used for randomization.
- Conversion of weight to kg: The following conversion rule is used:  
$$\text{Weight in Kilogramm} = \text{weight in Pounds} / 2.2$$
$$\text{Weight in Kilogramm} = \text{weight in oncs} / 35.27$$

The result is rounded to 2 decimals.
- Conversion of height to cm: The following conversion rule is used:  
$$\text{Height in Centimetres} = \text{Height in Feet} * 30.48$$
$$\text{Height in Centimetres} = \text{Height in Inch} * 2.54$$

The result is rounded to the unit (ie no decimal).
- Conversion of temperature to °C: The following conversion rule is used:  
$$\text{Temperature in } ^\circ\text{Celsius} = ((\text{Temperature in } ^\circ\text{Fahrenheit} - 32) * 5) / 9$$

The result is rounded to 1 decimal.

- Calculation of weight for age Z-score (WAZ) for each subject (rounded to 2 decimal):

$$WAZ = (\text{Weight of subject} - \text{median weight}) / \text{Standard deviation for weight}$$

- Calculation of height for age Z-score (HAZ) for each subject (rounded to 2 decimal):

$$HAZ = (\text{Height of subject} - \text{median height}) / \text{Standard deviation for height}$$

**11.3.4. Immunogenicity**

- For a given subject and given immunogenicity measurement, missing or non-evaluable measurements will not be replaced. Therefore, an analysis will exclude subjects with missing or non-evaluable measurements. Kinetics will be plotted on subjects with results available at all timepoints.
- The Geometric Mean Concentrations/Titres (GMC/Ts) calculations are performed by taking the anti-log of the mean of the log titre transformations. Antibody titres below the cut-off of the assay will be given an arbitrary value of half the cut-off of the assay for the purpose of GMT calculation.
- The 95% CI for the mean of log-transformed titer will be first obtained assuming that log-transformed values were normally distributed with unknown variance. The 95% CI for the GMTs/GMCs will be then obtained by exponential-transformation of the 95% CI for the mean of log-transformed titer.
- A seronegative subject is a subject whose antibody titre is below the cut-off value of the assay. A seropositive subject is a subject whose antibody titre is greater than or equal to the cut-off value of the assay.
- An exploratory definition of vaccine response to the RSV neutralising antibodies will be as:
  - At least a 4-fold increase from pre-vaccination if pre-vaccination neutralising antibody titre <128.
  - At least a 3-fold increase from pre-vaccination if pre-vaccination neutralising antibody titre in [128-256].
  - At least a 2.5-fold increase from pre-vaccination if pre-vaccination neutralising antibody titre in ]256-1024].
  - At least 1-fold from pre-vaccination if pre-vaccination neutralising antibody titre >1024

Please note that other definition of vaccine response will be also be explored but interest might be limited considering this is not target population.

- Assay cut-off for the humoral immunity will be per the following table

Component	Method	Unit	Cut-off
Respiratory Syncytial Virus A Ab	NEUTRALIZATION	ED60	8
Respiratory Syncytial Virus F protein Ab.IgG (Anti-RSV PreF antibody)	ELISA	EU/ml	10
Respiratory Syncytial Virus F protein Ab.IgG (Palivizumab competing Ab)	ELISA	µg/ml	9.6

- Considering the cut-off for the neutralising antibody against RSV-A is below the assay's LLOQ [32], the following rules will be applied for derivation of seropositivity status and GMT:

Assay	Raw result	Derivation for seropositivity status	Derivation for GMT calculation	Derivation for fold-increase between Post and Pre-vaccination titres
RSV-A neutralising Antibody	<cut-off	NEG	Cut-off/2	LLOQ/2
	[cut-off-LLOQ [	POS	Cut-Off	LLOQ/2
	≥LLOQ	POS	Exact value	Exact value

- The cut-off for the PCA assay is set at the level of the assay LLOQ (9.60 µg/mL). For results below the cut-off (LLOQ), an arbitrary value of half of the cut-off will be considered for calculation of GMC and fold increase.
- All CI computed will be two-sided 95% CI.
- CMI: CD4+ and/or CD8+ T-cells, by ICS using WBS
  - All results available in the database (events/per million of cells) will be dividing by 10000 in order to express the results in percentage (%).
  - The derived variable that will be used for the analysis will be:
    - the frequency of RSV F/N/M2-1 specific and combined (RSV F/N/M2-1) CD4+ T-cells expressing at least two marker among CD40L, IL-2, TNF-α, and IFN-γ;
    - the frequency of CD4+ and CD8+ T-cells expressing at least one or any combination of immune marker(s) among CD40L, 41BB, IL-2, TNF-α, IFN-γ, IL-13 and IL-17 upon stimulation with F, N and M2-1 peptide pools and combined peptide pools.
  - Those derived variables will be obtained as follows: sum of all specific responses of interest minus the sum of corresponding background responses. All values less or equal to zero will be set to 1 for the purpose of GM calculation.
  - Co-expression profile: for each CD4+/CD8+ any combination of markers, the RSV F/N/M2-1 specific response will be obtained by subtracting the background value to the RSV value (stimulation with RSV F/N/M2-1 peptides), and by setting to 1 all values less than or equal to zero for the purpose of GM calculation and graphical representation.
  - The log-transformation of the percentage of RSV F/N/M2-1 specific CD4+/CD8+ T-cells will be applied, and the GM calculations will be performed by taking the anti-log of the mean of the log transformations.
  - For calculation of Th2/Th1 ratio has to be done by taking average of Th2 and Th1 profile at the individual level after adjusting on background.

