**<each group>:**

- RSV-Ld = Low dose ChAd155-RSV vaccine (5 x 10^9 vp)
- RSV-Md = Middle dose ChAd155-RSV vaccine (1.5 x 10^10 vp)
- RSV-Hd = High dose ChAd155-RSV vaccine (5 x 10^10 vp)
- Placebo-Ld = Non-active control (0.5 ml)
- Placebo-Md = Non-active control (0.15 ml)
- Placebo-Hd = Non-active control (0.5 ml)
- N = number of subjects with pre and corresponding post-vaccination results available
- n/% = number/percentage of subjects with titre fold change meeting the specified criterion
- PI(D31) = Post-vaccination dose 1 at Day 31
- PII(D61) = Post-vaccination dose 2 at Day 61
- PII(D366) = Post-vaccination dose 2 at Day 366

**Template 41 Geometric mean of the individual ratio of anti-RSV-A neutralising antibody titers at each post-vaccination timepoint compared to pre-vaccination with 95% CI <PPS for analysis of immunogenicity at Day X>**

						GMT ratio			
								95% CI	
Group	N	Time point description	GMT	Time point description	GMT	Ratio order	Value	LL	UL
<each group>		PI(D31)		PRE		PI(D31) / PRE			
		PII(D61)		PRE		PII(D61) / PRE			
		PII(D366)		PRE		PII(D366) / PRE			

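### RSV-A neutralising titres from 8 to <32 enter the GMT as 8 but the fold increase as 16, so the GMT is low for that band and the GMTs in Template 41 will in general not reproduce the printed ratio

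*SAP*

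**What the plan says.** SAP 11.3.4 gives the cut-off as "Respiratory Syncytial Virus A Ab NEUTRALIZATION ED60 8". This lies below the assay's LLOQ, and the SAP introduces special handling for that reason: "LLOQ [32], the following rules will be applied for derivation of seropositivity status and GMT". The derivation table then has one column for the GMT and another for the fold increase:

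- Below the cut-off: "<cut-off NEG Cut-off/2 LLOQ/2", that is 4 for the GMT and 16 for the fold increase.
- From the cut-off to below the LLOQ: "cut-off-LLOQ [ POS Cut-Off LLOQ/2", that is 8 for the GMT and 16 for the fold increase.
- At or above the LLOQ: "POS Exact value Exact value", so the two columns coincide.

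Template 41 (SAP 13.2) has the title "Geometric mean of the individual ratio of anti-RSV-A neutralising antibody titers at each post-vaccination timepoint compared to pre-vaccination with 95% CI". Each row prints the post-vaccination GMT, the pre-vaccination GMT and a GMT ratio with its confidence interval. N is the number of infants with results at both time points. The template does not say which substitution feeds its two GMT columns, and no footnote says that the ratio may differ from their quotient. Protocol 11.6.3 leaves the handling of results below the LLOQ, for both quantities, to the SAP.

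**The concern.** Two things follow from having two columns.

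First, 8 is the floor of the 8 to <32 band. Putting every result in that band at its floor can only pull the GMT down.

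Second, on one set of paired infants with one substitution rule, the geometric mean of the individual ratios equals the quotient of the two GMTs exactly. With two rules that identity is lost. A reader of Template 41 sees two GMTs beside a column labelled as their ratio and may find that the division does not give the printed figure.

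Neutralising titre is a secondary endpoint (SAP 4.2), reported at baseline and Days 31, 61 and 366. What is at stake is how readable and accurate its summary tables are.

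**Working it through.** **Inputs.** Cut-off 8, LLOQ 32 and the substitutions above (SAP 11.3.4). About 16 infants per group, and about 8 at the permitted minimum in Steps 1 and 2 (SAP Table 1 footnote). The documents give no baseline titre distribution, so baselines below are assumptions.

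**Rules as functions.** For the GMT, g(x) = 4 if x < 8, 8 if 8 ≤ x < 32, otherwise x. For the fold increase, f(x) = 16 if x < 32, otherwise x. Let h = f/g, so h = 4 below 8, h = 2 from 8 to <32, and h = 1 from 32 up. For paired infants,

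(quotient of GMTs) / (printed ratio) = geometric mean over infants of h(pre)/h(post).

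This is 1 if nobody is below 32 or if each infant below 32 stays in the same band. It can otherwise equal 1 only if changes of band happen to offset each other.

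**One infant, 20 before and 40 after (true rise 2.0).** GMT rule: 40/8 = 5.0. Fold-increase rule: 40/16 = 2.5.

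**Group of n, with k below 32 at baseline only.** The factor is 2^(k/n) for the 8 to <32 band and 4^(k/n) for <8. The quotients below assume 256 before and 512 after for all other infants, and 512 after for the k infants too.

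| n | k and band at baseline | GMT quotient | Printed ratio | Factor |
|---|---|---|---|---|
| 16 | 0 | 2.000 | 2.000 | 1.000 |
| 16 | 1, 8 to <32 | 2.484 | 2.378 | 1.044 |
| 16 | 1, <8 | 2.594 | 2.378 | 1.091 |
| 16 | 4, 8 to <32 | 4.757 | 4.000 | 1.189 |
| 16 | 4, <8 | 5.657 | 4.000 | 1.414 |
| 8 | 1, 8 to <32 | 3.084 | 2.828 | 1.091 |

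Four of 16 in the 8 to <32 band at both visits: both figures are 1.682 and agree. Four of 16 moving from <8 to 8 to <32: 2.000 against 1.682, a factor of 1.189.

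**Direction of the GMT bias.** With 4 of 16 in the 8 to <32 band, the GMT is multiplied by (8/16)^(4/16) = 0.841 if their true titres are 16, and by nearly (8/32)^(4/16) = 0.707 if they are close to 32. Below 8 the direction is not fixed: 4 is half of a true 7.9 (factor 0.51) and twice a true 2.

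**Size under assumed baselines.** Log2-normal baseline, SD 1.5 / 2 log2 units, true 2.4-fold rise, 2 million draws. The last column is the error of the baseline GMT if 16 replaces both 4 and 8.

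| True GMT | Share <32 | Baseline GMT too low by | GMT quotient | Printed ratio | Error with 16 |
|---|---|---|---|---|---|
| 64 | 25% / 31% | 19% / 18% | 2.78 / 2.65 | 2.41 / 2.26 | -2% / +6% |
| 128 | 9% / 16% | 8% / 11% | 2.57 / 2.59 | 2.44 / 2.37 | -2% / +1% |
| 256 | 2% / 7% | 2% / 6% | 2.45 / 2.50 | 2.41 / 2.41 | -1% / -1% |
| 512 | 0.4% / 2% | 0.5% / 2% | 2.41 / 2.44 | 2.40 / 2.41 | 0% / 0% |

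**The case against.** The separate rule is deliberate and disclosed. It exists because this assay's cut-off lies below its LLOQ, and setting low baselines to 16 rather than 4 or 8 keeps the fold increase conservative. That stands, but it does not explain why the GMT should use the floor of the band.

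Template 41 prints one ratio and defines it. A second fold increase appears only if a reader divides the columns, and SAP 13 calls its mock displays illustrative. So the mismatch rests on reading the GMT column of the derivation table as the source of the GMTs in Template 41. That is the natural reading, but the template does not state it.

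Infants must be RSV-seropositive (Protocol 5.2), and the lowest titre band that the SAP tabulates is <128 (SAP 6.2.1.2). This suggests, without proving it, that few results fall below 32. Eligibility rests on a commercial ELISA and not on a neutralising titre, so such results are not excluded.

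Sampling error is also larger than the bias. With 16 infants and an SD of 1.5 to 2 log2 units, the 95% CI of a GMT runs from a factor of 2^(2.13×1.5/4) = 1.7 to 2^(2.13×2/4) = 2.1 either way. That limits the importance of the point but does not remove a systematic error.

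A reader might compare the palivizumab-competing assay, where one value serves both quantities, and infer an oversight. The comparison is weak: that assay's cut-off equals its LLOQ, so it has no intermediate band.

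**Conclusion.** The point holds in limited form. The GMT is biased down for results from 8 to <32. If Template 41 uses the GMT derivation, its row will in general not reconcile once an infant is below 32 at one visit only or changes band. The discrepancy is about 4% for one infant in 16 and 19% for four in 16, both in the 8 to <32 band at baseline only. Under the assumed baselines the GMT is low by 18-19% at a true GMT of 64, and by at most about 2% at 512. The actual share below 32 is unknown.

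Three stronger readings are not supported:

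- That the GMTs and the ratio can never agree. They agree exactly if nobody is below 32 or if no infant changes band.
- That all GMTs are biased down. Without results below 32 there is no effect, and 4 for a result <8 has no fixed direction of bias.
- That the plan exaggerates both the rise and a later decline to Day 366. The planned ratio uses 16, only the GMT summaries use 4 and 8, and the documents give no data on waning below 32.

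Immunogenicity analyses are within group (SAP 6.2.1) and all analyses are descriptive (SAP 7). No test or dose-escalation decision depends on these figures.

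**What to change.** In the derivation table of SAP 11.3.4, use LLOQ/2 (16) for every RSV-A neutralising result below 32 in both the GMT and the fold increase, and keep the cut-off of 8 for seropositivity status only. On paired infants the ratio then equals the quotient of the GMTs exactly. At minimum, compute the GMT columns of Template 41 with the fold-increase rule and say so in a footnote.

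The change is one column of one table. Its cost is that a result <8 is set to 16, which overstates it at least two-fold and no longer separates it from 8 to <32. For that reason, report the number of infants <8 and from 8 to <32 by group and visit. The fix makes the two figures consistent and reduces the GMT bias in most of the scenarios above, but it does not recover unquantifiable titres: the infant going from 20 to 40 would still read 2.5-fold.

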6.7.3. Laboratory assays

Please refer to Appendix A for a detailed description of the assays performed in the study. Please refer to Appendix B for the address of the clinical laboratories planned to be used for sample analysis.

The following laboratory assays are planned:

- Frequency of interleukin 2, 13, and 17 (IL-2, IL-13 and IL-17), cluster of differentiation 40 ligand (CD40L), 41BB, tumor necrosis factor alpha (TNF- α), and IFN- γ secreting CD3+/CD4+ and CD3+/CD8+ T-cells will be determined by ICS assay on whole blood samples (Table 8).
- Serostatus to RSV F and/or G protein will be determined at screening by ELISA commercial kit on serum sample, according to the manufacturer instructions (Table 9).
- Functional (neutralizing) antibody titers against RSV-A will be measured by a neutralization assay on serum samples (Table 9).
- RSV F protein antibody concentrations and palivizumab-competing antibody concentrations will be determined by in-house ELISA on serum sample (Table 9).

- RTI will be assessed by:
 - Quantitative RT-PCR that is able to discriminate RSV-A and RSV-B subtypes (Table 10).
 - Qualitative multiplex PCR for detection of a panel of viruses (Table 10).
 - Local RSV assay and local RVP where available (Table 10).

These assays will be performed at the investigator’s laboratory, at GSK Biologicals’ laboratory or at laboratory designated by GSK Biologicals using standardized and validated procedures.

Table 8 Cell-Mediated Immunity (CMI)

System	Component	Challenge	Method	Unit	Laboratory
Whole blood	IL-2, CD40L, 41BB, TNF- α , IFN- γ , IL-13, IL-17 secreting CD3+/CD4+ and CD3+/CD8+ T-cells	Peptide pools covering the proteins F, N & M2-1	ICS	Events/10E6 cells	GSK Biologicals ¹ or designated laboratory

CD40L: cluster of differentiation 40 ligand; **ICS**: Intracellular staining; **IFN- γ** : interferon gamma, **IL (IL-2; IL-13; IL-17)**: interleukin; **TNF- α** : tumor necrosis factor alpha

¹ GSK Biologicals laboratory refers to the clinical laboratory sciences (CLS) in Rixensart, Belgium; Wavre, Belgium.

Table 9 Humoral Immunity (Antibody determination)

System	Component	Method	Kit / Manufacturer	Unit	Cut-off	Laboratory
SERUM	Respiratory Syncytial virus Ab.IgG (RSV F or G antibody)	ELISA	IBL International	Qualitative assay (positive/negative)	Qualitative assay (positive/negative)	Q ² Solutions
SERUM	Respiratory Syncytial Virus A Ab	NEUTRALIZATION	In-house	ED60	To be defined	GSK Biologicals ¹ or NÉOMED-LABS

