### 6.2.1.1. CMI analysis

The analysis will be performed on each group separately, pooled placebo group and pooled RSV group. All the CMI analysis will be performed for each peptide pool (F, N, M2-1) separately and taking all the peptide pool together for subjects who has data available for the three peptide pools.

With respect to secondary objectives, the following parameters will be summarized by group using descriptive statistics (N, geometric mean [GM], minimum [min], 1st quartile [Q1], median, third quartile [Q3], maximum [max]), at each timepoint during which blood samples are collected for CMI in investigational sites with a laboratory in proximity capable to perform WBS necessary for the CMI assay:

- Frequency of CD4+ T-cells expressing at least two markers among CD40L, IL-2, TNF- $\alpha$ , and IFN- $\gamma$  upon stimulation with F, N and M2-1.
- Box plot with individual data for CD4+ T-cells expressing at least two markers among CD40L, IL-2, TNF- $\alpha$ , and IFN- $\gamma$  upon stimulation with F, N and M2-1 and combined peptide pool will be presented.

With respect to tertiary objectives, the cellular immune response will be further characterized using descriptive analysis of the frequency of CD8+ T-cells and CD4+ T-helper cell profile (Th1, Th2, Th17) expressing at least one or any combination of marker(s) among CD40L, 41BB, IL-2, TNF- $\alpha$ , IFN- $\gamma$ , IL-13, and IL-17.

The following parameters will be summarized by group using description statistics (N, GM, min, Q1, median, Q3, max), at each timepoint during which blood samples are collected for CMI:

- Frequency of CD4+ and CD8+ T-cells expressing at least one or any combination of immune marker(s) among CD40L, 41BB, IL-2, TNF- $\alpha$ , IFN- $\gamma$ , IL-13 and IL-17 upon stimulation with F, N and M2-1 peptide pools.
- Tabular presentation of T-helper cell 'Th1' profile - Frequency of CD4+ T-cells expressing at least IFN- $\gamma$  but no IL-13 upon stimulation with F, N and M2-1 peptide pools.
- Tabular presentation of T-helper cell 'Th2' profile: Frequency of CD4+ T-cells expressing at least IL-13 but no IFN- $\gamma$  upon stimulation with F, N and M2-1 peptide pools.
- Tabular presentation of T-helper cell 'Th17' profile - Frequency of CD4+ T-cell expressing atleast IL17 upon stimulation with F, N and M2-1 peptide pools.
- Calculation of 'Th2/Th1 ratio' = Frequency of Th2 T-cells / frequency of Th1 T-cells.

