- Separate box plot with individual data for CD4+ and CD8+ T-cells expressing at least one marker among CD40L, 41BB, IL-2, TNF- $\alpha$ , IFN- $\gamma$ , IL-13 and IL-17 upon stimulation with F, N and M2-1 and combined peptide pools will be presented.

- Separate box plot with individual data for CD4+ T-cells expressing at least IFN- $\gamma$  but no IL-13 (Th1 profile) upon stimulation with F, N and M2-1 and combined peptide pools will be presented.
- Separate box plot with individual data for CD4+ T-cells expressing at least IL-13 but no IFN- $\gamma$  (Th2 profile) upon stimulation with F, N and M2-1 and combined peptide pools will be presented.
- Separate box plot with individual data for CD4+ T-cells expressing at least IL17(Th17 profile) upon stimulation with F, N and M2-1 and combined peptide pools will be presented.

The need to generate co-expression profile graph for any combination for CD4+ and CD8+ will be evaluated after looking at the descriptive tables.

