RSV-Ld = Low dose ChAd155-RSV vaccine ( $5 \times 10^9$  vp)  
 RSV-Md = Middle dose ChAd155-RSV vaccine ( $1.5 \times 10^{10}$  vp)  
 RSV-Hd = High dose ChAd155-RSV vaccine ( $5 \times 10^{10}$  vp)  
 Placebo-Ld = Non-active control (0.5 ml)  
 Placebo-Md = Non-active control (0.15 ml)  
 Placebo-Hd = Non-active control (0.5 ml)  
 PRE= Pre-vaccination at Day 1  
 PI(D31) = Post-vaccination dose 1 at Day 31  
 PII(D61) = Post-vaccination dose 2 at Day 61  
 PII(D366) = Post-vaccination dose 2 at Day 366

Note: This graph is provided as an example. Template will be adapted to display the 3 RSV or 3Control groups together and the 4 timepoints: PRE, PI(D31), PII(D61) and PII(D366).

Please note – To present the information on pooled RSV and pooled Placebo after looking at the data of Day 61 analysis.

**Figure 6 Co-expression profile of the RSV <F/N/M2-1> specific <CD4+> T-cells expressing at least two markers among CD40L, IL-2, TNF- $\alpha$ , and IFN- $\gamma$  in <RSV-Ld group> <PPS for analysis of immunogenicity at Day X>**

RSV-Ld = Low dose ChAd155-RSV vaccine ( $5 \times 10^9$  vp)  
 RSV-Md = Middle dose ChAd155-RSV vaccine ( $1.5 \times 10^{10}$  vp)  
 RSV-Hd = High dose ChAd155-RSV vaccine ( $5 \times 10^{10}$  vp)  
 Placebo-Ld = Non-active control (0.5 ml)  
 Placebo-Md = Non-active control (0.15 ml)  
 Placebo-Hd = Non-active control (0.5 ml)

Note: This graph is given as an example. Template will be adapted to display Q1-Median-Q3 for each combination of at least 2 markers out of (CD40L, IL-2, TNF- $\alpha$ , and IFN- $\gamma$   $\rightarrow$  11 combinations) for each timepoint: PRE, PI(D31), PII(D61) and PII(D366). It will be generated for each vaccine group and each RSV pool of peptides (RSV F/N/M2-1).

**Template 43 Number and percentage of subjects with at least one RSV infection, RSV-RTI, RSV-LRTI, RSV-severe LRTI, RSV-very severe LRTI, All-cause LRTI and RSV hospitalization from vaccination dose 1 up to D366/D731 visit <Exposed Set>**

	Group N =					Total N =				
	n**	n	%	95% CI		n**	n	%	95% CI	
Categories	n**	n	%	LL	UL	n**	n	%	LL	UL
No Infection										
RSV infection - symptomatic or asymptomatic*										
RSV-RTI										
RSV-LRTI										
RSV-severe LRTI										
RSV-very severe LRTI										
All-cause LRTI										
RSV hospitalization §										

RSV-Ld = Low dose ChAd155-RSV vaccine (5 x 10^9 vp)

RSV-Md = Middle dose ChAd155-RSV vaccine (1.5 x 10^10 vp)

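### The cell-mediated immunity derivation sets non-positive values to 1 without a unit; as written, an infant with no net response enters the geometric mean as 1% of T-cells, 10,000 times a floor of 1 per million

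*SAP*

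**What the plan says.** The Protocol gives the assay unit in section 6.7.3, Table 8, as "Events/10E6 cells"; Appendix A also expresses results per million CD4+ or CD8+ T-cells.

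SAP section 11.3.4 then sets out the derivation in this order:

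- All database results "will be dividing by 10000 in order to express the results in percentage".
- The derived frequencies are the stimulated response minus background. "All values less or equal to zero will be set to 1 for the purpose of GM calculation".
- For the co-expression profile, background is subtracted "by setting to 1 all values less than or equal to zero for the purpose of GM calculation and graphical representation", so in this case the rule reaches the plots as well.
- The final step names the scale on which logs are taken: "The log-transformation of the percentage of RSV F/N/M2-1 specific CD4+/CD8+ T-cells will be applied". Back-transforming the mean log gives the GM.

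SAP section 6.2.1.1 lists the GM with N, minimum, quartiles, median and maximum for the secondary CD4+ endpoint and for the tertiary profiles (any marker, Th1, Th2, Th17). It leaves the co-expression graphs open: "The need to generate co-expression profile graph for any combination for CD4+ and CD8+ will be evaluated after looking at the descriptive tables". The note to Figure 6 in section 13.2 says of that graph: "Template will be adapted to display Q1-Median-Q3 for each combination of at least 2 markers".

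**The concern.** A replacement value exists so that a zero or negative net response can be logged and still count as low. On the per-million scale, 1 does that. On the percent scale, where the SAP has by then placed the data, 1 is a very high T-cell frequency, and infants without a response would pull the GM up.

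The other replacement rules in SAP sections 11.3.4 and 11.3.6 are tied to an assay limit (cut-off, LLOQ or LOD). Only the T-cell rule gives a bare number.

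The GM of a secondary endpoint is at stake. So is the GM of the Th2 profile: read literally, a group in which no infant has a net Th2 response would show a Th2 GM of 1%. Protocol section 1.1.3 names Th2 skewing as a hypothesised mechanism of enhanced RSV disease, so an artefact there would be especially unwelcome.

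**Working it through.** **Conversion.** 1% of 1,000,000 cells is 10,000 cells, so per million divided by 10,000 gives percent. The SAP's conversion factor is correct. It follows that 1% = 10,000 per million and 1 per million = 0.0001%.

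**Size at one time point.** Let k of n infants have non-positive values and let the others have frequency r. Then GM = floor^(k/n) × r^((n−k)/n). The ratio of the two readings is 10000^(k/n), whatever r is:

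- 1 of 16: 10000^(1/16) = 1.78
- 2 of 8 or 4 of 16: 10000^(1/4) = 10
- 4 of 8 or 8 of 16: 10000^(1/2) = 100

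Example: with 4 of 16 non-positive and responders at 300 per million, the GM is 10000^0.25 × 300^0.75 = 721 per million as written, and 300^0.75 = 72 with a floor of 1 per million. Group sizes of about 8 (minimum, Steps 1 and 2) and about 16 come from Protocol section 3, Table 1. The values of k and r are assumptions.

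**Change over time.** For illustration, take 16 infants, with non-positive values falling from 12 to 4 and responder frequency doubling. With a floor of 10,000 per million, the pre GM is 10000^0.75 × r^0.25 and the post GM is 10000^0.25 × (2r)^0.75:

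| Responders, pre to post (per million) | GM pre | GM post | Post/pre |
|---|---|---|---|
| 100 to 200 | 3,162 | 532 | 0.17 |
| 300 to 600 | 4,162 | 1,212 | 0.29 |
| 1,000 to 2,000 | 5,623 | 2,991 | 0.53 |
| 3,000 to 6,000 | 7,401 | 6,817 | 0.92 |
| 5,000 to 10,000 | 8,409 | 10,000 | 1.19 |
| 10,000 to 20,000 | 10,000 | 16,818 | 1.68 |

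For a general floor F the ratio is 2^0.75 × (r/F)^0.5. With F = 10,000 it equals 1 at r = 10000/2^1.5 = 3,536 per million (0.35%). Below that, a rise in both the number and the level of responders shows as a fall.

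**Sensitivity to the floor.** For 300 to 600 per million the same formula gives 29, 9.2 or 2.9 with F = 1, 10 or 100 per million. If the non-positive count stays at 4 of 16, the ratio is 2^0.75 = 1.68 for any floor.

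**Co-expression graphs.** Here the floor also applies to what is plotted. With n = 16 and all responders below 1%, the replaced values are the largest in the group. The plotted third quartile is then 1% once 5 or more values are non-positive, and the median is 1% once 9 or more are.

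**The case against.** The 1% reading is probably not what was intended. The SAP list consists of bullets, not numbered steps, and neither bullet containing the rule mentions percent. On the raw scale 1 is an ordinary small floor, and a program that replaces values before dividing would give the intended GM. Two of the SAP's example figures may also carry an axis unit that the available text does not show. This stands as a statement of likely intent. It does not supply the unit: no visible text places the 1 on the per-million scale, and the steps on either side of it are in percent.

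The time-change table is a chosen scenario, and the SAP does not tabulate post/pre GM ratios for T-cell data; it does so only for antibodies. That stands too. The table shows what a reader would see when comparing the printed GMs. The 10000^(k/n) inflation at a single time point does not depend on the scenario.

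Extreme cases would reveal themselves. In every row with a ratio below 1, both GMs exceed the highest responder value, and Template 42 prints the unreplaced maximum in the same table. With one or two replaced values and a normal spread among responders, the error would be much harder to see.

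Finally, the immunogenicity analysis is descriptive and within group, no decision rule uses the GM, and the co-expression graphs are optional. This limits the consequence but does not make the statistic right.

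**Conclusion.** The concern holds. As written, the rule replaces a null response with 1%, and the GM exceeds the one obtained with a floor of 1 per million by a factor of 10000^(k/n). That factor follows from the SAP's own steps. Two things are assumed: that most responder frequencies are below 1%, which is needed for non-responders to raise the GM, and that non-positive values occur often enough to matter. The documents give neither figure for infants. The replacement rule itself anticipates non-positive values, and Protocol section 1.1.6 reports no vaccine-induced CD4 response by this assay in adults.

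The effect is confined to the GM of the secondary CD4+ endpoint and of the tertiary profiles, and to the co-expression graphs if they are produced. The point should be corrected before the first T-cell tables are programmed, because two programmers could follow the present text and differ by orders of magnitude.

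**What to change.** After the sponsor confirms the intended floor, state in both bullets of SAP section 11.3.4 (derived variables and co-expression profile) that the background-subtracted value is set to 1 event per million when it is zero or negative, and that this is done before division by 10,000, so that the floor is 0.0001% on the reported scale. Add the number of non-positive values beside each GM in the T-cell tables. The count is not needed to settle the unit, but it lets the reader judge how far the GM depends on the floor.

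The cost is one line in each of two bullets, the matching line in the derivation program, and one count row in the tables.
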